3.2 Exclusion Criteria

Subjects meeting any of the criteria below may not participate in the study:

1. A history of, or a concurrent, clinically significant illness, medical condition or laboratory abnormality that, in the investigator's opinion, could affect the conduct of the study.

2. Active infection requiring systemic therapy
3. Pregnant or breastfeeding (**NOTE:** breast milk cannot be stored for future use while the mother is being treated on study).
4. Known additional malignancy that is active and/or progressive requiring treatment; exceptions include basal cell or squamous cell skin cancer, in situ cervical or bladder cancer, or other cancer for which the subject has been disease-free for at least two years.
5. Active central nervous system (CNS) lymphoma
6. Major surgery or radiation therapy within 28 days of study registration
7. Uncontrolled infectious disease, including active herpes simplex or herpes zoster
8. Known positive test for Hepatitis B surface antigen, Hepatitis C, or HIV. NOTE: testing is not required.
9. Known GI disease or GI procedure that could interfere with the oral absorption or tolerance of oral medications including difficulty swallowing, as determined by the treating physician.
10. Evidence of uncontrolled cardiovascular conditions, including uncontrolled hypertension, cardiac arrhythmias, symptomatic congestive heart failure, unstable angina, or myocardial infarction within the past 6 months.
11. Q-T interval, based on Bazett-corrected interval > 0.48 sec
12. Treatment with any investigational drug within 21 days prior to registration or within 5 times the half-life of the investigational drug.
13. Peripheral neuropathy \geq grade 2
14. Prior treatment with bortezomib, ixazomib, or romidepsin.
15. Systemic treatment, within 14 days of Cycle 1 Day 1, with strong inhibitors of CYP1A2 (fluvoxamine, enoxacin, ciprofloxacin), strong inhibitors of CYP3A (clarithromycin, telithromycin, itraconazole, voriconazole, ketoconazole, nefazodone, posaconazole) or strong CYP3A inducers (rifampin, rifapentine, rifabutin, carbamazepine, phenytoin, phenobarbital), or use of St. John's wort. See section 5.5.2.
16. Any serious medical or psychiatric illness that could, in the investigator's opinion, potentially interfere with the completion of treatment according to this protocol.
17. Known allergy to any of the study medications, their analogues, or excipients in the various formulations of any agent.

18. Prior autologous hematopoietic stem cell transplant within 60 days of study registration.

19. Prior allogeneic hematopoietic stem cell transplant.

4. SUBJECT REGISTRATION

All subjects must be registered through Big Ten CRC Administrative Headquarters' electronic data capture (EDC) system. A subject is considered registered when an On Study date is entered into the EDC system.

Subjects must be registered prior to starting protocol therapy. Subjects must begin therapy within **5 business days** of registration.

5. TREATMENT PLAN

Single arm phase I/II study of ixazomib and romidepsin in relapsed/refractory PTCL.

5.1 Phase I Dose Escalation Study

The phase I study includes three dose levels. Each cycle is 28 days. Patients will continue to receive therapy until progressive disease, unacceptable toxicity, or if any other withdrawal criteria are met.

Dose level	Romidepsin	Ixazomib
4 (start)	10mg/m ² IV on days 1, 8, 15	4 mg PO on days 1, 8, 15
5	14mg/m ² IV on days 1, 8	4 mg PO on days 1, 8, 15
6	14mg/m ² IV on days 1, 8, 15	4 mg PO on days 1, 8, 15

Dose assignments during phase 1 will be made according to the TITE-CRM design⁸². The first patient enrolled will be assigned to dose level 4. Subsequent patients will be assigned to a dose level based on the estimated probability of DLT (as determined by a statistical model; see Section 12.1 for details). Each patient will be assigned to a dose level as he/she is enrolled (based on the information available at the time). A new patient does not have to wait for previous patients to complete the first cycle before being assigned to a dose level. However, to ensure safety, no patient will be assigned to dose level 5 or 6 until at least one patient has completed the first cycle at dose level 4 with no DLTs.

Enrollment will continue until either (i) 18 patients have been treated at one dose level, and the next enrolled patient would also be assigned to that dose level, or (ii) a total of 36 patients have been enrolled across all dose levels combined.

The estimated MTD is the dose level with a model-estimated rate of DLT closest to 25% (but not more than 33%) after 36 patients have been enrolled (or the dose level where 18 patients have been treated, and the next enrolled patient would also be assigned to that dose level).

NOTE: After the first six patients have completed the first cycle, if the estimated rate of DLT at dose level 4 exceeds 0.33, the trial will stop for toxicity.

5.2 Phase II Study

The (up-to) 18 patients treated at the estimated MTD from phase I will comprise the interim analysis of a 2-stage phase II study of efficacy. If at least 3 of the (up-to) 18 patients have a CR, we will proceed to the second stage of the phase II (where 12 patients will be enrolled).

The phase II study will include treatment with ixazomib and romidepsin at the MTD established in the Phase I study. Each cycle is 28 days and patients will receive treatment until progressive disease, unacceptable toxicity, or if any other withdrawal criteria are met.

5.3 Pre-medication and Hydration

Pre-medications: dexamethasone 12mg PO/IV prior to romidepsin, as per institutional standards. Anti-retroviral prophylaxis with acyclovir or a similar medication is recommended to start with initiation of therapy following local guidelines.

5.4 Romidepsin + Ixazomib Administration

Drug	Dose ¹	Route	Schedule ²	Cycle Length
Romidepsin	10-14mg/m ²	Intravenously (IV) as per institutional standard	Days 1, 8, 15 or Days 1, 8	28 days
Ixazomib	2.3-4 mg	PO after romidepsin ³	Days 1, 8, 15	

¹ Body surface area (BSA) should be recalculated when weight changes by $\geq 10\%$ according to local guidelines.

² A window of +/- 3 days may be applied to all study visits to accommodate observed holidays, inclement weather, scheduling conflicts etc. Date and time of each drug administration should be clearly documented in subject's chart and electronic case report forms (eCRFs).

³ Ixazomib should be taken once a week on the same day (± 3 days as above) for the first three weeks of a four-week cycle. There should be at least 72 hours between doses. Ixazomib should be taken at least one hour before or at least two hours after food. The whole capsule should be swallowed with water. The capsule should not be crushed, chewed or opened. If vomiting occurs after taking a dose, the patient should not repeat the dose. The patient should resume dosing at the time of the next scheduled dose.

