6.2 Dose Modifications

Dose modifications below are outlined for the Phase I portion of the trial. Further information on the Phase II dose modification will be determined after the MTD is established.

Treatment with romidepsin and ixazomib will use a cycle length of 28 days. Missed doses within a cycle will not be made up. For example, if drug is held on Day 8 and given the next week, the day of administration will be Day 15; Day 8 will be considered as missed. Once a dose of romidepsin or ixazomib is reduced, the dose may only be re-escalated after discussion with and approval by the sponsor investigator. If a delay occurs on day 1 of a cycle, then day 1 will be when the first dose of a cycle is given.

For a new cycle of treatment to begin or resumption of treatment within a cycle, the patient must meet the following criteria:

- ANC $\geq 1,000/\text{mm}^3$.
- Platelet count $\geq 75,000/\text{mm}^3$.
- Concurrent magnesium and potassium supplementation is allowed to maintain levels within a normal range.
- All other nonhematologic toxicity (except for alopecia) must have resolved to \leq Grade 1 or to the patient's baseline condition.

Hematologic toxicities:

Toxicity	Action
Within-Cycle (day 8 and 15) Dose Modifications 
 • If platelet count $< 30 \times 10^9/\text{L}$ or ANC $< 0.50 \times 10^9/\text{L}$ on treatment days 8 and 15 (for dose adjustments on day 1, see below). 	
 • Hold treatment • Obtain CBC with diff 2x/week until platelet count or ANC have reached goal outlined above • Upon recovery, reinitiate treatment at 1 dose level reduction as per section 6.3.
Dose Modifications for Subsequent Treatment Cycles 
 • ANC $< 1.0 \times 10^9/\text{L}$, platelet count $< 75 \times 10^9/\text{L}$ on day 1 of a cycle. 	
 • Hold romidepsin and ixazomib until resolution as per criteria above • Obtain CBC with diff 2x/week until platelet count or ANC have reached goal outlined above • Upon recovery, reinitiate treatment at 1 dose level reduction as per section 6.3. • The maximum delay before treatment may be discontinued is 21 days and at the discretion of the local PI.

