⁵Archival tissue confirming disease relapse (after initial or any subsequent salvage therapy) is requested at screening. If archival tissue is unavailable or insufficient, a biopsy is mandatory. FFPE for IHC testing, RNA-Seq, WES, and HTS must be available. Verification of sufficient tissue is required prior to C1D1. Biopsy samples will include FFPE and snap frozen tissue for analysis. See CLM for collection, processing, labeling and shipping instructions.

⁶Vital signs to include temperature, blood pressure, heart rate, respiratory rate. Height at screening only.

⁷EKGs will also be obtained if Zofran or other 5-HT₃ serotonin receptor antagonists are used as anti-emetics. In this instance, EKGs should be performed at least 2 weeks after initiation of the medication to assess the QT interval

⁸CBC to include white blood cell count, hemoglobin, hematocrit, platelets, differential

⁹CMP to include sodium, potassium, chloride, creatinine, blood urea nitrogen, glucose, AST, ALT, total bilirubin, alkaline phosphatase, total protein, albumin, magnesium and lactate dehydrogenase (LDH).

¹⁰Laboratory assessments for cycles 1-3.

¹¹Perform if abnormal transaminases are present

¹²Perform if patient has risk factors for HIV

¹³For women of childbearing potential (WOCBP): urine or serum β hCG, within 14 days prior to study registration. If a urine test is positive or cannot be confirmed as negative, a serum pregnancy test will be required.

¹⁴Tumor imaging to continue pre-Cycle 3 and 5 and then every 3 cycles thereafter until 24 months after initiation of study treatment, and then every 6 cycles, or until disease progression or at time of suspected clinical progression.

¹⁵Must be performed within 60 days of C1D1. If the bone marrow is positive and the PET is negative for bone marrow uptake, then a confirmatory bone marrow biopsy will be repeated at the time of first radiographic CR. If the bone marrow is positive and the PET is positive for bone marrow uptake, then a bone marrow biopsy is not required at the time of first CR.

¹⁶Romidepsin and ixazomib administration per dosing cohort from Phase I. Ixazomib is not given on Day 15 for dose levels 1 and 2. Romidepsin is not given on Day 15 for dose level 5. See 6.3.

¹⁷[removed]

¹⁸PBMC and plasma for future MRD assessments at Pre-Treatment C1D1, C3D1, C5D1, and at every timepoint for response assessment.

¹⁹Whole blood is to be collected at Pre-Treatment C1D1 for somatic baseline.

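### Section 5.4 schedules ixazomib on Days 1, 8 and 15 across its whole 2.3-4 mg range, while Section 6.3 and calendar footnote 16 omit Day 15 at reduction levels 2 and 1

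*Combined protocol and SAP*

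**What the plan says.** Four places in the protocol bear on ixazomib dosing days.

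- **Section 5.4, administration table and footnote 3.** The ixazomib row spans 2.3-4 mg and lists Days 1, 8, 15 only. Footnote 3 describes weekly dosing (± 3 "days as above) for the first three weeks of a four-week cycle". Neither names an exception by dose level or refers to 6.3. The romidepsin row of the same table does list alternatives: "Days 1, 8, 15 or Days 1, 8".
- **Section 6.3, reduction table.** Levels 6, 5, 4 and 3 have ixazomib on Days 1, 8, 15. Level 2 (3 mg) and level 1 (2.3 mg) have it on Days 1 and 8. Romidepsin is 10 mg/m² on Days 1, 8, 15 at levels 4, 3, 2 and 1.
- **Section 7, study calendar, footnote 16.** "Ixazomib is not given on Day 15 for dose levels 1 and 2". The footnote is attached to the ixazomib row and to its Day 15 cell, and it refers the reader to 6.3.
- **Section 6.2.** Patients move down the levels by instructions such as "Upon recovery, reinitiate treatment at 1 dose level reduction as per section 6.3".

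Section 5.1 assigns phase I patients to levels 4, 5 or 6, all with ixazomib on Days 1, 8, 15.

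**The concern.** Section 5.4 is where the protocol says how the two drugs are given, and its dose range reaches down to the reduced strengths. Because the romidepsin row lists two schedules, a reader can reasonably take the single ixazomib schedule as complete. The 2.3 mg strength makes this plainest: in 6.3 it appears only at level 1, on Days 1 and 8, so 5.4 pairs it with a schedule that 6.3 never uses for it.

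What is at stake is whether a Day 15 capsule is planned for patients at levels 2 and 1. Counting from the assigned levels, level 2 is two reductions below level 4, three below level 5 and four below level 6. These patients would generally have had at least two dose-level reductions already, usually for toxicity. No clause says which section prevails if the two are read differently.

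**Working it through.** The plan gives no per-cycle total to reproduce, so the check is a direct count from the two schedules.

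**Inputs.** Dose and days at each level come from 6.3. The alternative schedule, Days 1, 8, 15 at any dose from 2.3 to 4 mg, comes from the 5.4 ixazomib row and footnote 3.

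**Formula.** Planned ixazomib per 28-day cycle = mg per dose × number of dosing days.

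| Level | Romidepsin per cycle (6.3) | Ixazomib, 6.3 days | Ixazomib, 5.4 days |
|---|---|---|---|
| 6 | 14 × 3 = 42 mg/m² | 4 × 3 = 12 mg | 4 × 3 = 12 mg |
| 5 | 14 × 2 = 28 mg/m² | 4 × 3 = 12 mg | 4 × 3 = 12 mg |
| 4 | 10 × 3 = 30 mg/m² | 4 × 3 = 12 mg | 4 × 3 = 12 mg |
| 3 | 10 × 3 = 30 mg/m² | 3 × 3 = 9 mg | 3 × 3 = 9 mg |
| 2 | 10 × 3 = 30 mg/m² | 3 × 2 = 6 mg | 3 × 3 = 9 mg |
| 1 | 10 × 3 = 30 mg/m² | 2.3 × 2 = 4.6 mg | 2.3 × 3 = 6.9 mg |

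**Where they differ.** Levels 3 to 6 agree. At level 2 the ratio is 9/6 = 1.50, and at level 1 it is 6.9/4.6 = 1.50. Either way the difference is one extra dose per cycle.

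**Step from level 3 to level 2.** On the 6.3 days, ixazomib falls from 9 to 6 mg (6/9 − 1 = −33.3%). On the 5.4 days it stays at 9 mg. Romidepsin is 30 mg/m² at both levels, and the ixazomib strength is 3 mg at both, so the Day 15 ixazomib dose is the only thing that separates them in 6.3.

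**Step from level 2 to level 1.** The fall is −23.3% on either schedule (4.6/6 − 1 and 6.9/9 − 1), because only the strength changes.

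**The case against.** The strongest reply is that the level-specific text already settles the matter. Section 5.4 defines no dose levels; it gives ranges and cannot be used to dose anyone without 5.1 or 6.3. A site places a patient at level 2 or 1 by opening 6.3, where Days 1 and 8 stand in the same row as the dose. Section 6.2 orders reductions by reference to 6.3, and footnote 16 appears at the calendar cell where Day 15 dosing is read. On this view 5.4 is a general summary, and its footnote is worded as advice.

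Most of this stands, and it limits the point. In particular, a reader might infer that the protocol's reduction from level 3 to level 2 is no reduction at all, or that patients at levels 2 and 1 will receive 50% more ixazomib than intended. The documents do not support either inference. Both results follow only if a site takes the level from 6.3 and then follows the 5.4 days over 6.3 and footnote 16. In 6.3 itself the step is a real one, from 9 to 6 mg.

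The reply does not remove the conflict, for four reasons.

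- 5.4 is an operative dosing section, it names the 2.3 mg strength, and it carries neither the exception nor a cross-reference.
- Section 7.2.2 has both drugs given on Days 8 and 15 according to the dosing cohort. That does not help here, because all three assigned cohorts include Day 15 ixazomib.
- Not every reduction in 6.2 names 6.3: one ixazomib-specific neuropathy row calls for the next lower dose without citing the table.
- 6.3 is titled for phase I, and 6.2 leaves phase II modifications to be set once the MTD is known, whereas 5.4 has no phase limit. Until those rules are written, the Day 15 exception is less clearly in force in phase II.

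**Conclusion.** The inconsistency is real and confined to reduction levels 2 and 1. If a site dosed from 5.4, planned ixazomib per cycle would be 9 rather than 6 mg at level 2, equal to level 3, and 6.9 rather than 4.6 mg at level 1. These are planned amounts that assume no missed doses, and they are conditional on 5.4 being followed over two more specific provisions that agree with each other. Most sites would probably omit Day 15. The documents do not say how many patients would reach these levels; it is likely to be a small subset.

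A reader might also extend the point to the phase I dose assignments or the trial's operating characteristics. The documents give no ground for that: 5.1, 5.4 and 6.3 agree on the ixazomib schedule for levels 4, 5 and 6, and no effect on sample size, type I error or power is claimed. The point should still be corrected, because it concerns a dosing rule with a safety bearing for patients who have already needed reductions, and nothing in the protocol says which section governs.

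**What to change.** Reconcile the ixazomib row and footnote 3 of Section 5.4 with Section 6.3 and calendar footnote 16, so that the ixazomib days at each reduced level are stated consistently. Add a cross-reference from 5.4 to 6.3. When the phase II modification rules are written, state there whether the same level-specific schedules apply. Which schedule stands at levels 2 and 1 is for the clinical team; this review takes no position on it.

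The cost is wording in one table row and one footnote, plus a notice to sites. No design parameter or analysis changes.

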5.5 Concomitant Medications

5.5.1 Allowed Concomitant Medications

All treatments the investigator considers necessary for a subject's welfare may be administered at the discretion of the investigator in keeping with the community standards of medical care.

The following medications and procedures are permitted during the study:

- Antiemetics, preferably non- 5-HT₃ serotonin receptor antagonists may be used at the discretion of the investigator. The dose and regimen will be according to institutional

guidelines. If 5-HT₃ serotonin receptor antagonists are required to nausea refractory to initial agents, then monitoring the QT interval is necessary with periodic EKGs.

- IV fluids should be given to prevent volume depletion.
- Potassium and magnesium supplements
- Growth factors (e.g., granulocyte colony stimulating factor [G-CSF], granulocyte macrophage-colony stimulating factor [GM-CSF], recombinant erythropoietin) are permitted. Their use should follow published guidelines and/or institutional practice. Erythropoietin will be allowed in this study. Their use should follow published guidelines and/or institutional practice.
- Patients should be transfused with red cells and platelets as clinically indicated and according to institutional guidelines.
- Concomitant treatment with bisphosphonates will be permitted, as appropriate.
- Patients who experience worsening neuropathy from baseline may be observed for recovery and have dose reductions/delays as indicated in the protocol, and any supportive therapy or intervention may be initiated as appropriate at the discretion of the investigator.
- Supportive measures consistent with optimal patient care may be given throughout the study.
- Warfarin or Coumarin derivatives are allowed; however, prolongation of the PT and elevation of INR has been observed in patients receiving concomitant romidepsin and warfarin.

Refer to section on Supportive Care to ensure it is reconciled with allowed concomitant medications.

5.5.2 Prohibited Concomitant Medications

Systemic treatment with any of the following metabolizing enzyme inhibitors is not permitted during this study.

- A DDI with a strong inhibitor would increase romidepsin exposure.
 - Strong inhibitors of CYP1A2: fluvoxamine, enoxacin, ciprofloxacin
 - Strong inhibitors of CYP3A or P-gp: clarithromycin, telithromycin, itraconazole, voriconazole, ketoconazole, nefazodone, posaconazole, atazanavir, indinavir, nelfinavir, ritonavir, saquinavir.

Systemic treatment with any of the following metabolizing enzyme inducers should be avoided unless there is no appropriate alternative medication for the patient to use. A DDI with a strong inducer would decrease ixazomib exposure.

- Strong CYP3A inducers: rifampin, rifapentine, rifabutin, carbamazepine, phenytoin, and phenobarbital
 - Use of rifampin is not permitted as it *increases* the exposure to romidepsin and this is likely due to rifampin's inhibition of an undetermined hepatic uptake process that is predominantly responsible for the disposition of romidepsin. It is unknown if other potent CYP3A4 inducers alter the exposure of romidepsin.
- The dietary supplement St John's wort is not permitted.

The following procedures are prohibited during the study:

- Any antineoplastic treatment except for drugs in this treatment regimen.
- Radiation therapy (the requirement for local radiation therapy generally indicates disease progression).

- Platelet transfusions to meet eligibility criteria are not allowed within 3 days before study drug dosing.
- Adjuvant hormone therapy for breast or prostate cancer.

Examples of inhibitors, inducers, and substrates can be found in Appendix III and at <http://medicine.iupui.edu/clinpharm/ddis/table.aspx>.⁶⁴

5.6 Supportive Care

5.6.1 Romidepsin

Treatment with romidepsin has led to myelosuppression, infections, electrocardiographic changes, and tumor lysis syndrome. Management regarding these events is outlined below and please refer to standard guidelines for management.

Myelosuppression

Treatment can cause thrombocytopenia, leukopenia (neutropenia and lymphopenia), and anemia. Monitor blood counts regularly during treatment with romidepsin, and modify the dose as described in Section 6.2.

Electrocardiographic Changes

Several treatment-emergent morphological changes in EKGs (including T-wave and ST-segment changes) have been reported in clinical studies. The clinical significance of these changes is unknown. In patients with congenital long QT syndrome, patients with a history of significant cardiovascular disease, and patients taking anti-arrhythmic medicines or medicinal products that lead to significant QT prolongation, consider cardiovascular monitoring of EKGs at baseline and periodically during treatment. Confirm that potassium and magnesium levels are within normal range before administration of romidepsin.

Tumor Lysis Syndrome

In patients with Stage III/IV disease and/or high tumor burden are at greater risk for tumor lysis syndrome and should be closely monitored, and managed as per standard guidelines.

Nausea and/or Vomiting

Antiemetics: prefer that non-5-HT₃ serotonin receptor antagonists be used at the discretion of the investigator. The dose and regimen will be according to institutional guidelines. If 5-HT₃ serotonin receptor antagonists are required for to nausea refractory to initial agents, then monitoring the QT interval is necessary with periodic EKGs.

Fluid deficits should be corrected before initiation of study drug and during treatment.

